8. OBJECTIVE

The objective of this long-term safety study is to determine the nature, severity and frequency of the AE rate, the Cutaneous Safety Assessment and the Local Tolerability Assessment of S5G4T-1 when applied once daily, if applicable, for up to 52 weeks

The safety endpoints to be assessed include the following:

- The frequency of both local and systemic adverse events
- Investigator Cutaneous Safety Assessment (dryness and scaling) and Local Tolerability Assessment (itching and burning/stinging) at Baseline and at all study visits.

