Patients who completed Phase 3 studies SGT-54-01 or SGT-54-02 will be admitted into the study after the Entry Criteria have been met and an ICF has been signed. Qualified patients will receive study product at Baseline visit and treated for up to 40 weeks. New patients will be admitted into the study after the Inclusion/Exclusion Criteria have been met. At each visit, the patients will be assessed for a 5-point scale IGA of rosacea. If a patient is assessed as “clear” (0) or “almost clear” (1), the patient will not be dispensed the study product. If a patient is assessed as “mild”, “moderate” or “severe” (2, 3 or 4, respectively), study product will be dispensed, and the patient will use the study product daily according to patient instructions. Rosacea Quality of Life Questionnaire (RosaQoL) will be completed at Baseline, Visits 5, 8, 11, 14 and at End of Study or at early termination. The RosaQoL data of patients who were enrolled from SGT-54-01 or SGT-54-02, will be used from the questionnaire completed at Visit 6/Week 12 of SGT-54-01 or SGT-54-02. At each visit, the following safety measures will be recorded: monitoring for any AE including local and systemic; Investigator Cutaneous Safety Assessment rating of erythema and dryness, scaling and Local Tolerability Assessments rating of itching and burning/stinging on a scale ranging from 0 (None) to 3 (Severe).

A urine pregnancy test is required at all Visits for all females of child-bearing potential.

Clinical Evaluations will be performed at:

1. Visit 1/Screening, only applies for new patients

2. Visit 2/Baseline, Day 1 can also be Visit 6/Week 12, Day 85 of Study SGT-54-01 or Study SGT-54-02
3. Visit 3/Week 4, Day 29 (\pm 10 Days)
4. Visit 4/Week 8, Day 57 (\pm 10 Days)
5. Visit 5/Week 12, Day 85 (\pm 10 Days)
6. Visit 6/Week 16, Day 113 (\pm 10 Days)
7. Visit 7/Week 20, Day 141 (\pm 10 Days)
8. Visit 8/Week 24, Day 169 (\pm 10 Days)
9. Visit 9/Week 28, Day 197 (\pm 10 Days)
10. Visit 10/Week 32, Day 225 (\pm 10 Days)
11. Visit 11/Week 36, Day 253 (\pm 10 Days)
12. Visit 12/Week 40, Day 281 (\pm 10 Days)/ End of Treatment/End of Study for patients who complete the study, early terminate, or if the Sponsor terminates the study prematurely (applies only to patients who completed Study SGT-54-01 or Study SGT-54-02)

Applies for new patients:

13. Visit 13/Week 44, Day 307 (\pm 10 Days)
14. Visit 14/Week 48, Day 337 (\pm 10 Days)

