18.3. Analysis of Efficacy

This study is not intended to assess efficacy, but rather the IGA is included to determine the need for treatment and subsequent re-treatment after treatment course (in either Study SGT-54-01 or Study SGT-54-02 or for new patients not previously enrolled in Study SGT-54-01 or Study SGT-54-02) and any subsequent 4-week courses, if applicable. Certain efficacy data and endpoints will, however, be summarized.

Descriptive statistics will be used to summarize the assessment of efficacy. IGA scores will be summarized at Baseline Visit of Study SGT-54-01 or Study SGT-54-02 or at the Screening visit of SGT-54-07 for those patients not previously enrolled in Study SGT-54-01 or Study SGT-54-02, and entry into the study (SGT-54-07) and every 4 weeks through end of the study. The number and percentage of patients who achieve treatment success at the scheduled study visits will be tabulated.

The number of retreatments is defined as the number of clinical confirmations of the condition for which the subject was initially treated after the first treatment period with S5G4T-1. For rollover subjects previously treated with Vehicle Cream, this is the number after the initial treatment in Study SGT-54-07. For rollover subjects previously treated with S5G4T-1, this is the number of treatments in Study SGT-54-07 following the cessation of the treatment which began in Study SGT-54-01 or Study SGT-54-02.

The number of treatment free days until the first retreatment (relapse) will be calculated and analyzed. For rollover subjects previously treated with Vehicle Cream, the number of treatment free days will be the number of days between the end of the initial treatment in study SGT-54-07 and the start of the next treatment in study SGT-54-07 if one should be needed or the end of the subject's participation in study SGT-54-07. For rollover subjects previously treated with S5G4T1, the number of treatment free days will be the of days between the end of the initial treatment that began in Study SGT-54-01 or Study SGT-54-02 and the start of the next treatment in study SGT-54-07 if one should be needed or the end of the subject's participation in the study SGT-54-07.

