18.4. Safety Evaluation

Safety will be evaluated by tabulations of adverse events (AEs), Cutaneous Safety Assessments for dryness and scaling, Local Tolerability Assessment for itching and burning and assessments for erythema and telangiectasia will be presented with descriptive statistics at Baseline and at the scheduled study visits. Frequencies and percentages for each outcome category will be included in these statistics. Safety data will be presented for patients in the Safety Population with tabulations for the following periods 12 to 28 weeks, > 28 to 52 weeks and > 52 weeks to the end of the study, as well as an overall for all periods.

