8.1.2 Baseline Definition

Baseline is defined as the last non-missing assessment prior to first application in 54-01/02. For all subjects enrolled in 54-01/54-02, the baseline values from 54-01/54-02 will be considered the baseline values for calculations in 54-07. Missing results will not be flagged as baseline.

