8.1.3 Visit Windowing

For subjects receiving S5G4T-1 in 54-01/54-02, data from 54-01/54-02 will be included in summaries of 54-07. For subjects receiving vehicle in 54-01/54-02, baseline values will be sourced from 54-01/54-02 and data from follow-up visits of 54-07 will be used in summaries. The table below details the analysis visits to be summarized and the associated visits from 54-01/54-02 or 54-07 which will be sourced for each type of subject.

Analysis Visits for Efficacy and Safety Assessments

Analysis Visit	Subjects Receiving S5G4T-1 in 54-01/54-02	Subjects Receiving vehicle in 54-01/54-02
Week 4	54-01/02 - Week 4	54-07 - Week 4
Week 8	54-01/02 - Week 8	54-07 - Week 8
Week 12	54-01/02 - Week 12	54-07 - Week 12
Week 16	54-07 - Week 4	54-07 - Week 16
Week 20	54-07 - Week 8	54-07 - Week 20
Week 24	54-07 - Week 12	54-07 - Week 24
Week 28	54-07 - Week 16	54-07 - Week 28
Week 32	54-07 - Week 20	54-07 - Week 32
Week 36	54-07 - Week 24	54-07 - Week 36
Week 40	54-07 - Week 28	54-07 - Week 40
Week 44	54-07 - Week 32	Not available
Week 48	54-07 - Week 36	Not available
Week 52	54-07 - Week 40	Not available

Data from 54-07 will be mapped to the appropriate analysis visit described above based on nominal visit indications. Data from Early Termination (ET) and unscheduled visits will be determined using analysis visit windows. The analysis visit windows for ET and unscheduled visits are presented in the following table.

SGT-54-07 Analysis Visit Windows for Efficacy and Safety Assessments

Nominal Visit	Target Study Day¹	Window (Days)
Week 4	29	22 to 42
Week 8	57	43 to 70
Week 12	85	71 to 98
Week 16	113	99 to 126
Week 20	141	127 to 154
Week 24	169	155 to 182
Week 28	197	183 to 210
Week 32	225	211 to 238
Week 36	253	239 to 266
Week 40	281	267 to 294
Week 44	309	295 to 322
Week 48	337	323 to 350
Week 52	365	351 to 378

¹ Number of days since nominal Baseline visit of 54-07

Data collected at ET and unscheduled visits prior to study day 22 will not be analyzed. Data collected at ET and unscheduled visits after study day 378 will not be included in analyses.

The definition for the study day included in each study window is defined as below:

Study Day prior to Day 1 = Visit Date – Day 1 Date

Study Day on or after Day 1 = Visit Date – Day 1 Date + 1

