8.8.1 IGA

Descriptive statistics will be used to summarize the assessment of efficacy. IGA scores will be summarized at Baseline (see definition of baseline in Section 8.1.2) and every 4 weeks through end of the study. The number and percentage of patients who achieve treatment success at the scheduled study visits will be tabulated. A patient will be considered a success if their IGA score is clear or almost clear.

In addition to the above summary a by-subject listing of all IGA results will be presented.

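### For prior-vehicle patients, IGA and tolerability scores at entry into 54-07 reach no summary table, so change on vehicle cannot be separated from change after starting S5G4T-1

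*SAP*

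**What the plan says.** **Protocol.** Section 18.3 sets three kinds of time point for the IGA summary: the Baseline visit of the parent study, "and entry into the study (SGT-54-07) and every 4 weeks through end of the study". For the skin scores, section 8 names the assessments as safety endpoints, ending with "Local Tolerability Assessment (itching and burning/stinging) at Baseline and at all study visits", and section 18.4 says they "will be presented with descriptive statistics at Baseline and at the scheduled study visits". In the visit list of section 11, Baseline is a 54-07 visit: "Visit 2/Baseline, Day 1 can also be Visit 6/Week 12, Day 85 of Study SGT-54-01 or Study SGT-54-02". Both flow charts also use Baseline for 54-07 Visit 2, Day 1.

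**SAP.** Section 8.1.2 moves the reference point: "Baseline is defined as the last non-missing assessment prior to first application in 54-01/02". Section 8.1.3 adds: "For subjects receiving vehicle in 54-01/54-02, baseline values will be sourced from 54-01/54-02 and data from follow-up visits of 54-07 will be used in summaries". Section 8.8.1 then says "IGA scores will be summarized at Baseline (see definition of baseline in Section 8.1.2) and every 4 weeks through end of the study", with no mention of entry into 54-07. The shells of Tables 14.2.1.2 (IGA) and 14.3.1.1 (dryness, scaling, itching, burning/stinging) footnote Baseline as the parent-study value, and their next row is Week 4. Section 10 declares one change from the protocol, the removal of text about newly recruited patients. By-subject listings of all visits are kept (8.1.3, 8.8.1, 8.9.4.1, 8.9.4.2).

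**The concern.** Section 10 of the SAP states that no new patients were enrolled. Patients who had vehicle in 54-01/02 are therefore the only cohort whose first S5G4T-1 application falls inside this study. They are the natural place to see how skin scores move when the drug is started open-label, and that needs a tabulated value close to the start. The plan gives them a reference value from before a 12-week course of vehicle and then goes to 54-07 Week 4.

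This matters most for tolerability. Under protocol 15.1 and 15.2, dryness, scaling, itching and burning/stinging are recorded as adverse events only if they lead to temporary discontinuation of product, discontinuation from the study, or a new medication. Milder reactions appear only in these scores, so the adverse event tables cannot stand in for the missing row.

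**Working it through.** No figure in the plan needs reproducing. The check traces each scheduled 54-07 visit through the SAP 8.1.3 map.

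1. **Visits.** A rollover patient has entry (Visit 2) plus Weeks 4, 8, ..., 40 (Visits 3 to 12): 1 + 10 = 11 scheduled visits. Flow-chart footnote 2 says Visit 2 is the same visit as parent Visit 6 (Week 12).

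2. **Where each visit lands in the tables.**

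| 54-07 visit | Prior S5G4T-1 | Prior vehicle |
|---|---|---|
| Entry (= parent Week 12) | analysis Week 12 | not mapped |
| Week 4 | analysis Week 16 | analysis Week 4 |
| Weeks 8 to 36 | analysis Weeks 20 to 48 | analysis Weeks 8 to 36 |
| Week 40 | analysis Week 52 | analysis Week 40 |
| **Tabulated** | **1 + 10 = 11 of 11** | **0 + 10 = 10 of 11** |

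The one visit missing for the prior-vehicle group is entry.

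3. **Can another rule recover it?** The 13 windows in 8.1.3 apply to early-termination and unscheduled visits. The first runs from Day 22 to Day 42, so Day 1 falls in none.

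4. **Age of the remaining reference value at entry.** The parent Week 12 visit is Day 85, with a window of ± 4 days:
   - nominal: 85 − 1 = 84 days
   - earliest: (85 − 4) − 1 = 80 days
   - latest: (85 + 4) − 1 = 88 days

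   This takes the parent Baseline value as Day 1 and entry as the same day as parent Week 12. An earlier last non-missing value or a later entry would lengthen the gap.

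5. **What a reader can and cannot recover.** Let P be the share of patients in a given category at parent Baseline, E the share at 54-07 entry and A the share at a later 54-07 visit, all for the same patients. Then A − P = (E − P) + (A − E). The first bracket is the vehicle period and the second is the period after entry. The tables give P and A but not E, so only the sum can be formed.

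6. **What the shells print.** Tables 14.2.1.2 and 14.3.1.1 show n and category counts with percentages per visit; the IGA table adds success and failure. Neither has a change-from-baseline row.

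7. **Is entry the last look before S5G4T-1?** Not for everyone. Under protocol 14.1 and SAP 6.1, a patient who is clear or almost clear at a visit is not dispensed product. Such a patient starts S5G4T-1 later or not at all. Those who never start are outside the Safety Population, which needs at least one confirmed dose (SAP 8.4.1). For those who start later, the last pre-drug assessment may fall at a later visit, within a Week 4 or later row.

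**The case against.** The other side has real points.

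- **The SAP takes precedence and is open about its baseline.** Section 2 says it supersedes the protocol, section 8.1.2 defines the baseline, and the shells footnote it. That settles which text governs. It does not show that dropping the entry time point was intended, and section 10 does not list it.
- **Nothing is lost.** Entry scores stay in the by-subject listings. This is correct, and the point concerns tables only. Protocol 18.3 and 18.4 ask for summaries, which a listing does not provide.
- **The study is not meant to assess efficacy and has no inferential testing.** This lowers the stakes for IGA. It does not lower them for cutaneous safety and local tolerability, which are named safety endpoints in SAP 5 and 7.2.
- **Adverse events are anchored correctly.** SAP 8.9.2 treats vehicle-period events in this cohort as pre-treatment and counts periods from first S5G4T-1 application. This stands, but it covers local reactions only when they meet the reporting conditions in protocol 15.1 and 15.2.
- **The tolerability requirement is not spelled out.** Protocol 18.3 itself uses Baseline for the parent study and a separate phrase for entry into 54-07. So only the IGA requirement is explicit. The tolerability one rests on the visit list and flow charts.

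A reader might go further and infer that the tables will show irritation on S5G4T-1 as improvement, or will credit the drug with improvement that occurred on vehicle. The documents do not support that. The shells print no change, and neither document gives any figure for how scores moved on vehicle, so neither the direction nor the size of any distortion can be stated.

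**Conclusion.** The point holds for the tables. For prior-vehicle patients, a time point that the protocol requires explicitly for IGA, and by its own use of Baseline for tolerability, is missing from every summary table, and the SAP does not declare this as a change. The size is one of 11 scheduled 54-07 visits for this cohort and none of 11 for the prior-S5G4T-1 cohort. What remains is a reference row about 84 days (80 to 88) before entry, with a vehicle course in between. This assumes that entry coincides with parent Week 12 and that the parent Baseline value is from Day 1.

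No numerical bias is claimed. It would also be too strong to call the missing value the last skin state before S5G4T-1 for the whole cohort, because that is true only of patients dispensed product at Visit 2. The omission should be corrected, chiefly for the tolerability endpoint.

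**What to change.** - Add a row *54-07 entry (Visit 2)* to Tables 14.2.1.2 and 14.3.1.1, filled for the prior-vehicle column. A note can say that for prior-S5G4T-1 patients this visit is analysis Week 12.
- Keep the parent-study Baseline row.
- Footnote the new row: it is the last assessment before S5G4T-1 only for patients dispensed product at Visit 2, since patients clear or almost clear at entry start later or not at all. Key the footnote to actual dispensing at Visit 2.
- Align the visit map in SAP 8.1.3 and the time points in SAP 8.8.1. If the sponsor prefers to leave the row out, SAP 10 should declare and justify that.

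The cost is some SAP wording and one more row in two tables. The data are already collected at Visit 2 (protocol flow chart and 13.12), so nothing changes for sites or patients.

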8.8.2 Retreatments

The number of retreatments is defined as the number of clinical confirmations of the condition for which the subject was initially treated after the first treatment period with S5G4T-1. For rollover subjects previously treated with vehicle, this is the number of treatments after the initial treatment in 54-07. For rollover subjects previously treated with S5G4T-1, this is the number of treatments in 54-07 following the cessation of the treatment which began in 54-01 or 54-02. A clinical confirmation of the condition will be defined as IGA no longer being clear or almost clear after a previous IGA of clear or almost clear. When a subject has a clear or almost clear IGA in 54-07, it is expected they were instructed not to dose until the IGA reached mild, moderate or severe.

The number of treatment free days until the first retreatment (relapse) will be calculated and summarized. Relapse will be defined as a subject no longer having an IGA of clear or almost clear after a previous visit IGA of clear or almost clear. When a subject has a clear or almost clear IGA in 54-07, it is expected they were instructed not to dose until the IGA reached mild, moderate or severe. Number of treatment free days until first retreatment is defined as the number of days between an initial IGA assessment of clear or almost clear while the subject was receiving S5G4T-1 until an IGA of mild, moderate or severe.

For rollover subjects previously treated with vehicle, the number of treatment free days will be the number of days between the end of their first treatment of S5G4T-1 in 54-07 (when the subject has an IGA of clear or almost clear) and the start of the next treatment in 54-07 (when the

subject has an IGA indicating they should dose) if they treated with S5G4T-1 again or the end of the subject's participation in 54-07. For rollover subjects previously treated with S5G4T-1, the number of treatment free days will be the number of days between the end of the treatment that began in 54-01 or 54-02 (when the subject has an IGA of clear or almost clear) and the start of the next treatment in 54-07 (when the subject has an IGA indicating they should dose) if they treated with S5G4T-1 again or the end of the subject's participation in the 54-07.

Descriptive statistics for time to relapse (number of treatment free days until retreatment) and number of retreatments will be presented. A confidence interval (CI) for the median time to relapse will be presented using the Kaplan–Meier method. Patients who discontinue in 54-07 while not being treated and had not yet previously relapsed will be considered censored in the Kaplan–Meier analysis.

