7. EFFICACY AND SAFETY ENDPOINTS

7.1 Efficacy Endpoints

This study is not intended to assess efficacy.

IGA is included to determine the need for treatment and subsequent re-treatment after treatment course (in either Study SGT-54-01 or Study SGT-54-02) and any subsequent 4-week courses, if applicable. Certain efficacy data and endpoints will, however, be summarized.

The number of retreatments and the number of treatment free days until the first retreatment (relapse) will be calculated as described in Section [8.7.2.2](#).

RosaQoL will be completed at Baseline, Visits 5, 8, 11, 14, and End of Study. The RosaQoL data of patients who were enrolled from SGT-54-01 or SGT-54-02, will be used from the questionnaire completed at Visit 6/Week 12 of SGT-54-01 or SGT-54-02.

Erythema severity and telangiectasia assessments will be completed at each study visit.

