3 - Severe	xx (xx.x%)	xx (xx.x%)	xx (xx.x%)
Week 44^b			
n	xx	NA	xx
0 - None	xx (xx.x%)		xx (xx.x%)
1 - Mild	xx (xx.x%)		xx (xx.x%)
2 - Moderate	xx (xx.x%)		xx (xx.x%)
3 - Severe	xx (xx.x%)		xx (xx.x%)

^a Baseline is defined as the baseline value from SGT-54-01/SGT-54-02.

^b Table summaries based analysis visits, representing time from first dose of E-BPO 5% Cream.

SOURCE: USERNAME\SPONSOR\PROJECT\JOBNAME (DATE,TIME)

Table 14.2.4: Summary of Telangiectasia Assessment at Each Evaluation
(Safety Population)
(Page 5 of 5)

Telangiectasia Assessment	SGT-54-01/SGT-54-02 Vehicle Cream (N=xxx)	SGT-54-01/SG-54-02 E-BPO 5% Cream (N=xxx)	SGT-54-07 E-BPO 5% Cream (N=xxx)
Week 48 ^b			
n	xx	NA	xx
0 - None	xx (xx.x%)		xx (xx.x%)
1 - Mild	xx (xx.x%)		xx (xx.x%)
2 - Moderate	xx (xx.x%)		xx (xx.x%)
3 - Severe	xx (xx.x%)		xx (xx.x%)
Week 52 ^b			
n	xx	NA	xx
0 - None	xx (xx.x%)		xx (xx.x%)
1 - Mild	xx (xx.x%)		xx (xx.x%)
2 - Moderate	xx (xx.x%)		xx (xx.x%)
3 - Severe	xx (xx.x%)		xx (xx.x%)

^a Baseline is defined as the baseline value from SGT-54-01/SGT-54-02.

^b Table summaries based analysis visits, representing time from first dose of E-BPO 5% Cream.

SOURCE: USERNAME\SPONSOR\PROJECT\JOBNAME (DATE,TIME)

Table 14.2.5: Summary of Reoccurrence
(Safety Population)

	E-BPO 5% Cream (N=xxx)
Number of Retreatments	
n	xx
Mean	xx.x
SD	xx.xx
Median	xx.x
Min. to Max.	xx to xx
Number of Treatment Free Days Until First Retreatment	
n	xx
Median ^c (days)	xx.x
95% Confidence Interval ^c	(xx.x, xx.x)

^a Number of retreatments is defined as the number of times a subject's IGA goes from clear or almost clear to mild, moderate or severe after the subject was clear or almost clear while receiving E-BPO 5% Cream.

^b Number of treatment free days until first retreatment is defined as the number of days between an initial IGA assessment of clear or almost clear while the subject was receiving E-BPO 5% Cream until an IGA of mild, moderate or severe.

^c Median and 95% confidence intervals based on Kaplan-Meier method.

SOURCE: USERNAME\SPONSOR\PROJECT\JOBNAME (DATE,TIME)

Table 14.3.0.1: Summary of Extent of Exposure
(Safety Population)
(Page 1 of 2)

	SGT-54-01/SGT-54-02 Vehicle Cream (N=xxx)	SGT-54-01/SG-54-02 E-BPO 5% Cream (N=xxx)	SGT-54-07 E-BPO 5% Cream (N=xxx)
Total Number of Days of Exposure			
n	xx	xx	xx
Mean	xx.x	xx.x	xx.x
SD	xx.xx	xx.xx	xx.xx
Median	xx.x	xx.x	xx.x
Min. to Max.	xx to xx	xx to xx	xx to xx
Total Number of Applications			
n	xx	xx	xx
Mean	xx.x	xx.x	xx.x

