			xxxx xx	xxxx x	xxxxxxxx	xx	xxx		
			xxxx xx	xxxx x	xxxxxxxx	xx	xxx		
			xxxx xx	xxxx x	xxxxxxxx	xx	xxx		
			xxxx xx	xxxx x	xxxxxxxx	xx	xxx		xxxxxxxxxxxxxxxx
			xxxx xx	xxxx x	xxxxxxxx	xx	xxx		
			xxxx xx	xxxx x	xxxxxxxx	xx	xxx		
			xxxx xx	xxxx x	xxxxxxxx	xx	xxx		
			xxxx xx	xxxx x	xxxxxxxx	xx	xxx		xxxxxxxxxxxxxxxx
			xxxx xx	xxxx x	xxxxxxxx	xx	xxx		
			xxxx xx	xxxx x	xxxxxxxx	xx	xxx		
			xxxx xx	xxxx x	xxxxxxxx	xx	xxx		

¹ Day is calculated as date - Baseline date from SGT-54-07 for dates prior to Baseline visit. Otherwise, day is calculated as date - Baseline date + 1 for dates on or after Baseline visit. Day is only calculated for visits occurring in SGT-54-07.
² Determined by protocol-specified visit window for scheduled visits after Baseline. Only assessed for visits occurring in SGT-54-07.

SOURCE: USERNAME\SPONSOR\PROJECT\JOBNAME (DATE, TIME)

Listing sorted by Subject and Visit Number.

Listing 16.2.5.2: Subject Dosing Compliance
(Page xx of yy)

Subject	Age/Sex	Eval	Date of First Application	Date of Last Application	Number of Days of Exposure	Total Number of Applications	Number of Instructed Missed Applications ¹	Number of Non-Instructed Missed Applications ²
xxxxxx	xxxx	xxxxxxxx	xxxxxxxxxx	xxxxxxxxxx	xx	xxx	xx	xx
xxxxxx	xxxx	xxxxxxxx	xxxxxxxxxx	xxxxxxxxxx	xx	xxx	xx	xx
xxxxxx	xxxx	xxxxxxxx	xxxxxxxxxx	xxxxxxxxxx	xx	xxx	xx	xx
xxxxxx	xxxx	xxxxxxxx	xxxxxxxxxx	xxxxxxxxxx	xx	xxx	xx	xx
xxxxxx	xxxx	xxxxxxxx	xxxxxxxxxx	xxxxxxxxxx	xx	xxx	xx	xx

¹ The number instructed missed applications is the total number of missed doses on the CRF with reason "Per PI Instruction".

² The number of non-instructed missed applications is the total number of missed doses on the CRF with reason of "Other, specify reason".

SOURCE: USERNAME\SPONSOR\PROJECT\JOBNAME (DATE, TIME)

Listing sorted by Subject.

Listing 16.2.5.3: Subject Dosing
(Page xx of yy)

Subject	Age/Sex	Eval	Study Interval	Start Date	End Date	Number of Doses Applied ¹ or Number Of Doses Applied Each Day of the Date Span ²	Reason Subject Did Not Dose or Dosed More Than Once Per Day ²
xxxxxx	xxxx	xxxxxxxx	54-01 First to Last Dose Interval	xxxxxxxx	xxxxxxxx		
			54-01 Dosing Deviation	xxxxxxxx	xxxxxxxx	x	
			54-01 Dosing Deviation	xxxxxxxx	xxxxxxxx	x	
			54-01 Dosing Deviation	xxxxxxxx	xxxxxxxx	x	
			54-07 Dosing Interval	xxxxxxxx	xxxxxxxx	x	xxx xx xxxxxxxx
			54-07 Dosing Interval	xxxxxxxx	xxxxxxxx	x	
			54-07 Dosing Interval	xxxxxxxx	xxxxxxxx	x	xxx xx xxxxxxxx
			54-07 Dosing Interval	xxxxxxxx	xxxxxxxx	x	

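### SAP 8.8.2 gives treatment-free days before first retreatment two start points, and Table 14.2.5 carries only the one that may begin while an S5G4T-1 rollover is still on product

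*SAP*

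**What the plan says.** SAP 8.8.2 (Retreatments) gives a general definition for all subjects: "number of days between an initial IGA assessment of clear or almost clear while the subject was receiving S5G4T-1 until an IGA of mild, moderate" (severe also counts). It is not limited to 54-07 and does not mention stopping product.

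The next paragraph sets a rule for each cohort. For rollovers who had S5G4T-1 in the parent study, "the number of treatment free days will be the number of days between the end of the treatment that began in 54-01 or 54-02", running to the start of the next S5G4T-1 treatment in 54-07 or the end of participation. For vehicle rollovers the start is the end of their first S5G4T-1 treatment in 54-07. Protocol 18.3 also starts at the end of treatment and has no counterpart to the general sentence.

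For the retreatment count in S5G4T-1 rollovers, 8.8.2 says "this is the number of treatments in 54-07 following the cessation of the treatment which began in 54-01 or 54-02".

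The footnotes to Table 14.2.5 use the general wording. Footnote b defines the interval in these words: "number of days between an initial IGA assessment of clear or almost clear while the subject was receiving E-BPO 5% Cream until an IGA of" at least mild. Footnote a counts each occasion on which the "IGA goes from clear or almost clear to mild, moderate or severe after the subject was clear or almost clear while receiving" the product. Neither footnote names 54-07 or the end of treatment.

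SAP 7.1 says that the "number of treatment free days until the first retreatment (relapse) will be calculated as described in Section" 8.7.2.2. No such section exists; 8.7 covers procedures and therapies.

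**The concern.** A clear or almost-clear IGA and the end of treatment are the same event only if product stops at that visit. The SAP states this expectation for the extension alone: "When a subject has a clear or almost clear IGA in 54-07, it is expected they were instructed not to dose". If patients in the parent studies kept applying product after becoming clear, the general sentence starts the clock while they are still being treated.

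SAP 8.1.3 brings parent-study data for S5G4T-1 rollovers into the 54-07 summaries, with parent Weeks 4, 8 and 12 as analysis visits. A programmer working from footnote b could therefore start the interval at parent Week 4 or 8. A programmer working from the cohort rule would not start it before treatment stopped. The same patient would get two different values. Table 14.2.5 has a single pooled column, so its reader could not tell which patients were affected.

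**Working it through.** The plan states no figure for this variable, so there is nothing to reproduce. The check is date arithmetic on the visit schedule.

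**Inputs**
- Parent Week 12 is Day 85 and can be 54-07 Day 1 (SAP 6.1, Protocol 11).
- The parent Week 12 window is ±4 days (Protocol 12.1), so Day 81 to Day 89.
- Parent Weeks 4 and 8 are taken as Days 29 and 57. This is an assumption that follows the 54-07 schedule; the parent protocols are not supplied.
- 54-07 Week 4 is 28 days after 54-07 Day 1, so Day 85 + 28 = 113 on the parent scale.

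**Conditions**
1. Parent dosing continued to Week 12 whatever the IGA.
2. Parent-study IGAs enter this derivation.

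**S5G4T-1 rollover, clear or almost clear from the first such visit through parent Week 12, then mild or worse at 54-07 Week 4**

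General sentence and footnote b: relapse day minus day of first clear or almost-clear IGA. Cohort rule: relapse day minus end of parent treatment (Day 85).

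| First clear or almost clear | General sentence | Cohort rule | Difference |
|---|---|---|---|
| Parent Week 4 | 113 − 29 = 84 | 113 − 85 = 28 | 85 − 29 = 56 |
| Parent Week 8 | 113 − 57 = 56 | 113 − 85 = 28 | 85 − 57 = 28 |
| Parent Week 12 | 113 − 85 = 28 | 113 − 85 = 28 | 0 |

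The difference is time on product. With the Week 12 window it runs from 81 − 29 = 52 to 89 − 29 = 60 days for Week 4, and from 81 − 57 = 24 to 89 − 57 = 32 days for Week 8.

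**Change during parent dosing.** A patient who is clear at parent Week 4 and mild at parent Week 8 would, under the same two conditions, have a relapse at 57 − 29 = 28 days under footnote b and could be counted as retreated under footnote a. Under the cohort rule no interval has begun, because treatment has not stopped.

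**Vehicle rollover.** If product stops at the clear visit, the definitions agree: clear on 54-07 Day 57 and mild on Day 85 gives 28 days either way.

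**End point.** The general sentence ends at an IGA of mild or worse; the cohort rules end at the next treatment or the end of participation. These normally fall at the same visit, because product is dispensed there. They can part at the final visit: Protocol 17.4 lists Week 36 as the last dispensing visit for rollovers, so a first mild-or-worse IGA at Week 40 meets the relapse sentence but starts no further treatment.

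**The case against.** The strongest reply is that 8.8.2 already settles the start. SAP Section 10 says every enrolled subject came from a parent study, so the two cohort rules cover everyone, and a specific rule normally governs a general one. Both cohort rules tie the end of treatment to a clear or almost-clear IGA in parentheses. The general sentence directly follows the statement about not dosing in 54-07, and the variable is itself named for days off treatment. Footnote b may simply be shorthand.

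That may well be what the authors meant, but it is written nowhere. The footnote stands alone in the table shell. Protocol 18.3 cannot break the tie, because SAP Section 2 says the SAP supersedes the protocol where they differ.

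Two further objections stand as limits:
- Uninterrupted parent dosing is an inference. Protocol 11 speaks of 12 weeks of treatment, but it also describes 40 weeks in 54-07 as treatment although dosing there depends on the IGA. The synopsis's initial 12-week course also covers new patients, to whom the IGA rule applies. Listing 16.2.5.3 shows a "54-01 First to Last Dose Interval" with deviations, which fits continuous dosing but is only a layout.
- Entry of parent IGAs is the literal reading, not the only one. Table 14.2.5 lacks the analysis-visit footnote of the by-visit tables, and the cohort count of retreatments is limited to 54-07.

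A reader might infer that the reported median time to relapse will be overstated. The documents do not support that. They do not give the number of patients affected, and the general sentence can add short events during parent dosing as well as lengthen intervals. The pointer to 8.7.2.2 is a numbering slip and carries no weight beyond failing to resolve the conflict.

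**Conclusion.** The two start points are in the text, and the only planned table carries the one that is not tied to stopping product. If parent dosing ran the full 12 weeks and parent IGAs are used, 56 or 28 on-product days per affected patient are labelled treatment free, and a clear-to-mild change during parent dosing could be counted as a relapse or retreatment. Both conditions are inferred. Patients first clear at parent Week 12, and vehicle rollovers who stop at the clear visit, are unaffected.

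The point is minor: it concerns one descriptive table in a study not designed to assess efficacy. A reader might also infer a problem for the safety results, but no safety endpoint uses this variable.

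**What to change.** - Delete the general definition from 8.8.2 and from footnote b, and use the cohort rules in both. Keep their start (end of the first S5G4T-1 treatment, at a clear or almost-clear IGA), their end (start of the next S5G4T-1 treatment in 54-07, or end of participation) and the stated censoring.
- Limit the sentences in 8.8.2 that define clinical confirmation and relapse, and footnote a, to 54-07 visits after that treatment stopped. Parent-study IGA changes on treatment then neither start nor end an interval.
- State whether a first mild-or-worse IGA at the final visit, where no product is dispensed, is an event or is censored.
- Correct the pointer in SAP 7.1 from 8.7.2.2 to 8.8.2.

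The cost is wording in one SAP section, two footnotes and one cross-reference, plus one decision about the final visit. No new data are needed. The downside is that rollovers who are not clear at 54-07 entry contribute an interval only once they become clear and stop.
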